Primary Aim 2 is to make decisions about intervention components and component levels based on the factorial experiment results. We propose to use a modified version of a decision making approach frequently used in engineering (Wu & Hamada, 2000), which emphasizes main effects, using interactions as additional valuable information. This emphasis is consistent with our objective of identifying a set of components and component levels in which each component is making a detectable contribution to the overall effect, and any inactive components have been eliminated. We remind the reader that the mixed model analysis will be performed using effect coding, which will keep any covariances among main effects and interactions to a minimum. This makes it reasonable to start the decision making process by examining main effects, and then to consider interactions carefully in subsequent steps in the process. (Recall that our theoretical model does not predict any substantially-sized higher-order interactions, which is the basis for selection of the highly economical fractional factorial design. This Resolution V design enables examination of all two-way interactions.) The decision making process can be summarized as follows: Step 1: Initial tentative selection of components and component levels, consisting of identification of the components that show a significant main effect on the primary outcome variable, weight. If buddy training, recommended meal replacements, texting, or PCP report have a significant main effect, they will tentatively be selected for inclusion in the intervention. If there is a significant positive main effect of Number of Phone Coaching sessions, this is evidence that the more expensive level (24 sessions) performs better than the less expensive level (12 sessions), so it should be selected; otherwise, the less expensive level should be selected. Step 2: Consideration of interactions and final decision. Next we will examine interactions to look for any indication that we should consider reversing a decision made in Step 1. For example, suppose both Texting and PCP Report have significant main effects, so they were tentatively selected in Step 1. If there is a significant negative interaction between them, this means that the combined effect of Texting and PCP Report is less than the sum of the main effects. Suppose Texting has the larger main effect of the two. In that case we will start from the premise that Texting is selected, and then pose this question: When Texting is selected, *does PCP Report have a large enough incremental effect to justify its selection?* This question can be addressed by examining the simple effect of PCP Report when Texting is at the Yes level. Similar decision making logic will be used to examine all significant interactions that involve any components selected in Step 1 to arrive at the final decisions about selection of components and component levels. Step 3: Identifying the combination of components and levels that produces the largest effect that can be obtained for \$500 or less. If the costs associated with the combination of component and component levels selected in the process described above exceeds the upper limit of \$500, it will be necessary to consider less expensive versions of the intervention. Using as a starting point the set of components and component levels selected in Step 2, we will examine various scenarios in which we remove Yes/No components and change the levels of Either/Or components, and compute the expected outcome based on the regression parameters obtained in the statistical analysis to select the one with the largest expected effect that can be delivered for under \$500.

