5.2 Sample Size and Power

We base power on our primary endpoint: weight change from baseline to the 6-month timepoint. Our interest is in identifying the intervention components that make a more than minimal contribution to average weight loss, or conversely to identify those components that have minimal or no effect on weight loss. Our operational definition of more than minimal is a component effect size of .25 (mean difference divided by standard deviation). Thus, we have powered the study to detect effects of .25 or greater. Using the standard deviation estimate of 4 kg from Amundson et al (2009), which had a follow-up time similar to ours, this translates to a 1 kg difference in weight loss; we view weight loss of less than 1 kg as a minimal effect. There are five components in our 2^{5-1} fractional factorial design. Based on the minimal detectable effect size of .25, the total sample size will be 560 subjects. Based on our previous MBC and PDA+ studies, we conservatively assume an attrition rate of 10% at the 6-month timepoint, so that there will be approximately 504 subjects at this timepoint. Thus, each of the component main effect estimates will be based on 504 subjects, that is, 252 subjects in each of the two levels of the component. Based on these assumptions, we can detect a main effect or interaction effect size of .25 for each component with 80% power under a two-tailed hypothesis test.

Based on our current enrollment as of January 2017, approximately 45% of consented participants were eligible to be randomized after screening. We estimate that we will need to consent approximately 1250 subjects in order to obtain 560 eligible participants for randomization. Of the 560 eligible participants randomized, all will be asked to find a "Buddy" to participate in the study. We are estimating that approximately 850 "Buddies" will need to be verbally consented. (1250 participants + 850 Buddies = 2100 total to be consented).

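### The plan aims to identify components with minimal or no effect (under 1 kg), but its decision rules sort by significance and never compare an estimate with 1 kg

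*Combined protocol and SAP*

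**What the plan says.** Section 5.2 gives the trial two aims. One is to find components that contribute more than minimally to weight loss; the other is "or conversely to identify those components that have minimal or no effect on weight loss". It then fixes the boundary: "Our operational definition of more than minimal is a component effect size of .25", which at the assumed SD of 4 kg is 1 kg, and "we view weight loss of less than 1 kg as a minimal effect". The trial is sized on that figure, with "252 subjects in each of the two levels of the component" at 6 months, to detect it "with 80% power under a two-tailed hypothesis test". Alpha is not stated.

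The decision rules are in Section 5 under Primary Aim 2. Their declared purpose is a set in which "each component is making a detectable contribution to the overall effect, and any inactive components have been eliminated".

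- **Step 1** is "identification of the components that show a significant main effect on the primary outcome variable, weight". Coaching must have a significant positive effect, otherwise the 12-session level is taken. For the four Yes/No components only significance is mentioned.
- **Step 2** applies where an interaction is significant. Its worked example asks whether the second component would "have a large enough incremental effect to justify its selection". No number is given.
- **Step 3** applies only if the chosen set costs more than $500. It picks the affordable package with the largest expected effect.

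The 1 kg figure appears in none of the three steps. Section 5 does not mention confidence intervals.

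**The concern.** A non-significant result can arise in two ways. The interval may lie wholly below 1 kg, in which case the data support a minimal effect by the plan's own definition. Or it may include both 0 and 1 kg, in which case the data are compatible with no effect and also with the effect the trial was powered to find. The rules treat these two results alike, although only the first supports the second aim in Section 5.2.

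The same gap exists on the other side. A significant result shows an effect different from zero; it does not show one of 1 kg or more.

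What is at stake is what can be said about each component at the end. Later developers will read the unselected list as evidence about what can be left out, and part of that list may be unresolved.

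**Working it through.** **Inputs.** From Section 5.2: 560 randomised, 10% attrition, so 560 × 0.90 = 504 at 6 months, or 252 per level; SD 4 kg; threshold 0.25 × 4 = 1 kg; two-tailed test; 80% power. Assumed: two-sided alpha of 0.05.

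**The plan's own figure.** With 252 per level, a 1 kg difference and SD 4 kg, power is 80.0% (noncentral t, 502 df) at alpha 0.05. Alpha 0.01 would give 59% and alpha 0.10 would give 88%. So 0.05 is the conventional level that matches the stated power, and I use it below.

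**Precision of a main effect.** SE = 4 × √(2/252) = 0.356 kg. The 95% half-width is 1.96 × 0.356 = 0.70 kg, so an estimate is significant in the beneficial direction only above about 0.70 kg.

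**Zones for the estimate (kg of extra weight loss).**

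- The upper 95% limit falls below 1 kg when the estimate is below 1 − 0.70 = 0.30 kg.
- Between 0.30 and 0.70 kg the result is non-significant and the interval includes 1 kg.
- The lower 95% limit exceeds 1 kg only when the estimate is above 1 + 0.70 = 1.70 kg.

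**Chance of each result** (normal approximation). For a true effect d, the chance of landing between a and b is Φ((b − d)/SE) − Φ((a − d)/SE).

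| Result | d = 0 | d = 0.25 | d = 0.5 | d = 1 kg |
|---|---|---|---|---|
| Non-significant, upper limit below 1 kg | 78% | 55% | 29% | 2.5% |
| Non-significant, upper limit 1 kg or more | 17% | 34% | 42% | 17% |
| Significant benefit | 2.5% | 10% | 29% | 80% |
| Significant, unfavourable direction | 2.5% | 0.4% | 0.04% | about 0 |

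At a true effect of 1 kg, 17.4% + 2.5% = 19.9% of results are non-significant, and 17.4/19.9 = 87% of those have an interval that includes 1 kg.

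**Confidence level.** Whether the effect is below 1 kg is a one-sided question, so a 90% interval could be argued for. The cut for a minimal effect then moves to 1 − 1.645 × 0.356 = 0.41 kg, and the second row becomes 10%, 31% and 15% at 0, 0.5 and 1 kg.

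**Other sensitivities.** With no attrition (280 per level) SE = 4 × √(2/280) = 0.338 kg, the zone is 0.34 to 0.66 kg, and the 95% chance is 13% at 0 and 37% at 0.5 kg. If the SD were 5 kg (an assumption), SE = 5 × √(2/252) = 0.445 kg, the zone widens to 0.13 to 0.87 kg, and the chance is 36%, 60% and 36% at 0, 0.5 and 1 kg.

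**Step 2.** A simple effect at one level of another component uses half the data, about 126 per level: SE = 4 × √(2/126) = 0.504 kg, with a 95% half-width of 0.99 kg. Deciding by eye whether such an effect is large enough is harder still.

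**The case against.** The strongest reply is that Section 5 describes a selection procedure. Its standard is a detectable contribution, and a significance test applies that standard directly. In an optimisation framework that is legitimate, and nothing here argues against it. Nor is the threshold absent from the plan: 1 kg drives the sample size and, through it, the 0.70 kg cut-off. Stating 80% power also discloses that about 20% of true 1 kg components will be missed. The mixed model will produce estimates and standard errors, so intervals could be reported under the plan as written. All of this stands. It leaves open the second aim in Section 5.2, for which no rule says in advance how an estimate is to be read against 1 kg.

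A reader might infer more than the documents support:

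- **That non-significant components will be reported as inactive.** No passage says so. The phrase about eliminating inactive components comes close, but it describes the assembled package.
- **That significant harm could lead to selection.** Read literally, Step 1 asks for a beneficial direction for coaching only. But Primary Aim 1 speaks of improvement in weight loss, and the rest of Primary Aim 2 treats larger effects as benefit. This is a wording gap with little practical risk.
- **That selection is faulty because most selected components cannot exclude effects below 1 kg.** At a true effect of exactly 1 kg, a 95% interval lies wholly above 1 kg only 2.5% of the time at any sample size. That follows from testing at the threshold and is not a drafting error.

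The standard error here is a two-sample approximation. The planned model uses repeated weights, so its precision may differ somewhat.

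**Conclusion.** The point holds as one of interpretation and reporting. Section 5.2 seeks a conclusion of minimal or no effect, and the rules give no valid route to it, because they sort on significance without reference to 1 kg. Under the plan's own inputs, a component would be non-significant with a 95% interval still including 1 kg 17% of the time if inert, 42% if its true effect is 0.5 kg, and 17% if it is 1 kg. The 90% version is 10%, 31% and 15%. These figures rest on 252 per level, SD 4 kg and an assumed two-sided alpha of 0.05; a larger SD makes them worse. The finding does not call the selection rule, the sample size or the power into question.

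**What to change.** Keep the significance-based selection rule and add a few sentences to Section 5:

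1. State alpha. Define the effect as weight loss (baseline minus 6 months), active level or 24 sessions minus the other level. Require significance in the direction of greater weight loss for all five components.
2. Report every main effect, selected or not, with its confidence interval against 0 and 1 kg, and fix the confidence level in advance.
3. Describe an unselected component as having a minimal effect only if the upper limit is below 1 kg; otherwise call it inconclusive. For coaching, unselected means the 12-session level, as Step 1 already provides.
4. For selected components, state whether effects below 1 kg are excluded.
5. Do not select a component with a significant effect in the unfavourable direction. Report it with its interval, without labelling it harmful: if all five components were inert, at least one would show such a result about 12% of the time (1 − 0.975⁵, assuming independence).
6. Where Step 2 finds a significant interaction, report the relevant simple effects with intervals beside the main-effect description, since a small main effect can conceal a larger effect at one level of another component.

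The cost is wording, plus less tidy conclusions. At the 95% level about 17% of inert components and 42% of those with a true 0.5 kg effect would be reported as inconclusive. Most selected components would carry the statement that effects below 1 kg are not excluded, because excluding them needs an estimate above 1.70 kg. Sample size, power and the selection of beneficial components do not change.

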To apply the results obtained in Primary Aim 1 to build (1) an intervention made up of only active components and (2) if necessary, a second intervention that is optimized for scalability. Intervention (1) will be made up of the best set of components and component levels, based on the results of the experiment conducted in Primary Aim 1. Our conversations with private insurers suggest that in order to be scalable, Opt-IN needs to be implementable for \$500 or less. If Intervention (1) exceeds an estimated cost of \$500, we will identify the combination of components and component levels corresponding to the largest treatment effect that can be obtained for implementation costs of \$500 or less. This will be the new Opt-IN intervention.

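### Step 3 searches only within the Step 2 set, so it is not guaranteed to find the largest effect for $500 or less that Aim 2 promises

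*Combined protocol and SAP*

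**What the plan says.** Section 1.4 (Primary Aim 2) says that if the package of active components costs more than $500, "we will identify the combination of components and component levels corresponding to the largest treatment effect that can be obtained" within that limit, and that this will be the Opt-IN intervention.

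Section 5 sets out three steps.

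- Step 1 is the "identification of the components that show a significant main effect on the primary outcome variable, weight".
- Step 2 looks at interactions. Where two selected components have a significant negative interaction, the one with the larger main effect is kept and the other is questioned. In the plan's example: "does PCP Report have a large enough incremental effect to justify its selection"? What counts as large enough is not defined.
- Step 3 applies only if the Step 2 package costs more than $500. Its heading reads "Step 3: Identifying the combination of components and levels that produces the largest effect that can be obtained for" a sum within the $500 cap. The search takes the Step 2 package as its base. Its stated moves are: "we will examine various scenarios in which we remove Yes/No components and change the levels of Either/Or components". The version with the best predicted outcome from the fitted model is then chosen.

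The only either/or component is coaching (12 or 24 calls). No stated move adds back a Yes/No component.

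**The concern.** Step 2 judges a component conditionally: it may be dropped because it adds little while a stronger partner is present. Step 3 can then take the partner out because of its cost, or, where coaching is the partner, return to 12 calls. The reason for the exclusion has gone, but the exclusion remains. The set searched is then narrower than the set named in Aim 2 and in the Step 3 heading, even among components that showed a significant main effect.

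The situation is not far-fetched on the plan's own terms. Section 5 gives as an example two components that each have a main effect but add nothing when combined, and says the plan for such cases follows. At stake is which package is named Opt-IN. The Aim 1 estimates, the randomization and the error rates of the component tests are not affected.

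**Working it through.** **Inputs.** Costs are from Table 2 (Section 4.3.2). SD 4 kg, target effect 1 kg, 252 per level and 10% attrition are from Section 5.2. Two inputs are assumed because the plan does not give them: two-sided alpha 0.05, and 1 kg as the Step 2 cutoff for a large enough incremental effect (varied below).

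**1. The plan's own figures reproduce.**
- SE of a component difference = 4 × √(2/252) = 0.356 kg.
- Power for 1 kg = Φ(1/0.356 − 1.96) = Φ(0.85) = 0.80.
- 504/0.90 = 560 randomized.
- Minimum cost 281.67 + 86.52 = $368.19.
- Maximum cost 368.19 + 86.52 + 34.88 + 29.96 + 68.82 = $588.37.

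**2. How often the cap can bind.** The room above the minimum is 500 − 368.19 = $131.81. A package exceeds it if it contains any of:
- 24 calls + buddy: 86.52 + 68.82 = $155.34
- 24 calls + PCP + meal replacements: 86.52 + 34.88 + 29.96 = $151.36
- PCP + meal replacements + buddy: 34.88 + 29.96 + 68.82 = $133.66

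That is 6 of 16 packages ignoring texts, which cost $0, and so 12 of 32 in all.

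**3. A worked case (effects assumed).** Main effects: 24 calls 1.0 kg, PCP 1.0 kg, buddy 1.2 kg; PCP-by-buddy interaction −1.0 kg; the rest zero. With effect coding and the interaction on the main-effect scale, a component's simple effect is main + interaction when the partner is present and main − interaction when it is absent. PCP adds 1.0 − 1.0 = 0 kg with buddy and 1.0 + 1.0 = 2.0 kg without. Buddy without PCP adds 1.2 + 1.0 = 2.2 kg. Step 2 therefore keeps 24 calls + buddy and drops PCP.

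| Package | Gain over 12 calls alone | Cost | Status |
|---|---|---|---|
| 24 calls + buddy | 1.0 + 2.2 = 3.2 kg | $523.53 | Step 2 choice, over the cap |
| 24 calls alone | 1.0 kg | $454.71 | reachable in Step 3 |
| 12 calls + buddy | 2.2 kg | $437.01 | reachable, best in Step 3 |
| 24 calls + PCP | 1.0 + 2.0 = 3.0 kg | $489.59 | in budget, no stated route |

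The shortfall is 3.0 − 2.2 = 0.8 kg.

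**4. The shortfall moves with the assumptions.** Take instead 24 calls 1.0, buddy 1.0, PCP 0.8 and coaching-by-PCP −0.8 kg. Step 2 again keeps 24 calls + buddy. Step 3's best is 24 calls alone, 1.0 + 0.8 = 1.8 kg. Buddy + PCP with 12 calls gives 1.0 + 1.6 = 2.6 kg at $471.89, again 0.8 kg better. Change coaching to 1.5 and buddy to 0.8, and it becomes 2.3 against 2.4 kg, a shortfall of 0.1 kg.

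**5. Simulation of Steps 1 to 3** (20,000 trials per setting; two-way model; SE 0.356 kg for each effect). The full search covers all combinations of components that passed Step 1. Main effects are as in item 3.

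| PCP × buddy | Step 2 cutoff | Choice differs, all trials | Mean true loss, all trials |
|---|---|---|---|
| −1.0 kg | 1 kg | about 24% | about 0.18 kg |
| −1.0 kg | 0 kg | about 15% | about 0.11 kg |
| −0.5 kg | 1 kg | about 10% | about 0.08 kg |
| −0.25 kg | 1 kg | about 4% | about 0.03 kg |
| 0 | 1 kg | about 1.5% | about 0.01 kg |

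In the first row Step 3 is triggered in 55% of trials, the choice differs in about 44 to 45% of those, and the true loss when it differs is about 0.75 kg: 0.55 × 0.44 = 0.24, and 0.24 × 0.75 = 0.18 kg.

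**The case against.** The strongest reply is that the text is a summary and can be read flexibly. It calls the Step 2 set a starting point and speaks of various scenarios. The Step 2 exclusion rests on the premise that the partner is selected, so if Step 3 removes the partner, an analyst could ask the Step 2 question again. Nothing forbids this. But nothing provides for it either, and deciding it after the estimates are known would make the choice post hoc.

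A second reply is that some restriction is deliberate: Section 5 wants every retained component to make a detectable contribution. This stands as a reason for keeping out components that failed Step 1. It does not justify excluding one that passed Step 1 and was dropped only as redundant.

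A third reply is that the problem is rare and small. It needs a package over $500, a strong negative interaction, and removal of the partner (or a return to 12 calls) on cost. Section 5.2 treats differences below 1 kg as minimal. This largely stands and sets the severity.

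A reader might infer that Step 3 can only remove components, or that it cannot find the best package. The documents support neither. The coaching level may also change, and in the adverse case simulated, the written rule matches the full search in 55 to 56% of the trials that trigger Step 3. A reader might also take 0.8 kg as the expected loss. The documents give no such figure; it belongs to one assumed pattern of effects.

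**Conclusion.** The point holds as a gap between the stated objective and the stated search: Step 3 is not guaranteed to reach the largest effect for $500 or less, because a component dropped at Step 2 has no stated way back. The average loss over all simulated trials runs from about 0.01 kg with no interaction to about 0.18 kg with strong antagonism. In the strong case it is about 0.75 kg in the roughly one trial in four where the choice differs. These figures rest on the assumed effects, alpha 0.05, SD 4 kg and the assumed Step 2 cutoff. Severity is moderate. The wording should be settled before results are seen, but it does not threaten the trial's validity, and any omitted package can be scored later from the same fitted model.

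**What to change.** Reword Step 3. When the Step 2 package costs more than $500, compute the predicted 6-month weight loss (from the fitted model) and the cost (from Table 2) for every combination of the components that passed Step 1, including any dropped at Step 2, with coaching at either level. Choose the largest predicted loss among those costing $500 or less, and report the whole table.

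Components without a significant main effect stay out, in line with the aim of keeping only active components. So that objective and search agree, word the objective in Section 1.4 and in the Step 3 heading as the largest expected effect for $500 or less among components that passed Step 1.

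The cost is a few sentences in Sections 1.4 and 5 and a table of at most 32 rows. No new data, visits or model are needed.

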1.5 Secondary Exploratory Aim

To improve understanding of how the five intervention components work and of differential response to intervention components by conducting analyses based on the data from the experiment in Primary Aim 1. The analyses will examine the following mediators of weight loss: (a) hypothesized: adherence to treatment, and (b) exploratory: social-cognitive variables (self-efficacy, self-regulation, supportive accountability, and facilitation). To investigate whether certain intervention components are more or less effective in certain subgroups, we will examine moderation by conducting analyses separately for subgroups defined by gender, ethnicity, and BMI categories. We will also conduct latent class analysis to identify latent subgroups and predictors of subgroup membership. The results will inform subsequent research aimed at developing interventions tailored and optimized for these subgroups.

2 Background

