3.3.2 Inclusion Criteria

Eligibility Criteria. Enrollees will be adults between ages 18 and 60 with BMI 25-40. At least half will be female; half will be ≥ 45 years of age. They must be weight stable (no loss or gain ≥ 25 lbs for the past 6 months), not enrolled in any formal weight loss program or taking anti-obesity medications, but interested in losing weight. Candidates must own a Smartphone (Android or iOS) and be willing to install our Opt-IN app so that their data can be transmitted wirelessly to a study coach. They must be able to use the app to record dietary intake, physical activity, and weight onto the Smartphone. Prior to participating in any study procedure, they must voluntarily

provide informed consent. “Buddy” participants must be at least 18 years old, have access to a computer and internet, be willing to undergo “Buddy Training” and participate in 4 webinars, and be willing to provide support and encouragement to the participant.

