4.1.3 Recruitment of Minorities/ Low SES Participants

The Chicago metropolitan area is racially, ethnically, and socio-economically diverse. Of the entire sample, we plan to recruit 55% non-Hispanic Whites, 22% African Americans, 9% Hispanics, 4% other minority (45% minority). Our experience indicates that targeted recruitment of minorities has not been necessary to attain substantial, representative minority enrollment because the Chicago area population is so diverse. However, in the event that these minority groups are not adequately represented in our sample, we plan to target media outlets that are specific to these various ethnic groups.

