All of the estimated main effects and interactions will be based on all 32 experimental conditions. For example, the main effect of Number of Coaching Sessions will be estimated by comparing the mean of Experimental Conditions with 12 coaching calls in Table 3 vs. the mean of Experimental Conditions with 24 coaching calls. Similarly, the main effect of PCP report will be estimated by comparing the mean of Experimental Conditions having PCP progress reports sent vs. the mean of Experimental Conditions not having PCP progress reports sent. Note that in each case, all experimental subjects are included in the estimate. That is why factorial experiments can have small sample size/condition and still have excellent power if the overall sample size is sufficiently large.

Primary Aim 1 is to test for differences in weight by intervention components across the timepoints (baseline, 3- & 6-months), under an intent-to-treat basis, using linear mixed models. For each of the five components, we will determine whether there is a difference in change across time using baseline as the reference cell (i.e., 3-months vs baseline and 6-months vs baseline). From one perspective this is a main effect of each component on the pre-post difference. However, statistically these effects will be modeled as component by time interactions, with the 6-month outcome as the primary endpoint. We will also include two way interactions between components (e.g., Component 1 by Component 2 by time interaction). We note that (a) testing 2-way interactions between intervention components is extremely novel, as traditional RCTs are not capable of looking at these effects, and (b) because we will be using effect (-1,1) coding rather

than dummy (0,1) coding, the power for tests of main effects and interactions are identical for effects of identical size. We expect that testing these effects will be valuable, as we may find, e.g., that two intervention components each have independent main effects, but that when combined they offer no incremental effect. Our plan for dealing with such cases is elaborated below.

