
Secondary Aim (Mediation & Moderation). 1. Mediation analysis conducted on the data from a RCT enables the examination of the mediated effects of the intervention as a package. In contrast, we will be able to fit models specifying *which* intervention component is mediated by each putative mediator, where the putative mediators are (a) adherence (treatment attendance; diet, activity, and weight self-monitoring adherence), (b) supportive accountability (therapeutic alliance, autonomy support), (c) self-efficacy (diet, activity), (d) self-regulation (restraint,

disinhibition, autonomous motivation), (e) facilitation. We will test the mediation effects for significance using the general approach described in MacKinnon.⁴³ 2. Moderation analysis. To improve the field's understanding of differential response to individual intervention components we will conduct analyses separately for subgroups (e.g. men and women; different age and ethnic groups; different categories of BMI) to investigate whether certain intervention components are more effective or less effective in certain subgroups. We will also use latent class analysis to explore the data for latent subgroups, and will fit models predicting latent subgroup membership. The results will inform subsequent research aimed at developing interventions tailored to and optimized for these subgroups.

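### Exploratory moderation by observed characteristics rests on separate subgroup analyses, with no estimate, interval or test of the difference in component effects between subgroups

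*Combined protocol and SAP*

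**What the plan says.** Section 1.5 states that "we will examine moderation by conducting analyses separately for subgroups defined by gender, ethnicity, and BMI categories". The Secondary Aim paragraph of section 5 repeats the method and adds age: "we will conduct analyses separately for subgroups (e.g. men and women; different age and ethnic groups; different categories of BMI". The stated purpose is "to investigate whether certain intervention components are more effective or less effective in certain subgroups", and the use is given as "The results will inform subsequent research aimed at developing interventions tailored to and optimized for these subgroups".

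The other places that could supply a between-subgroup comparison do not:

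- The mixed model in section 5 has interactions, but only among components: "We will also include two way interactions between components (e.g., Component 1 by Component 2 by time interaction". The decision steps for Primary Aim 2 use those same interactions.
- Section 5.2 says "we can detect a main effect or interaction effect size of .25 for each component with 80% power under a two-tailed hypothesis test". Read with the effect-coding text in section 5, this refers to component-by-component interactions.
- The Secondary Aim also plans a latent class analysis. As described, it looks for latent subgroups and models who belongs to them. It does not compare component effects by gender, age, ethnicity or BMI.
- The mediation half of the same paragraph says effects will be tested for significance. The moderation half gives no rule.

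**The concern.** Moderation is a statement about a difference: the component effect in one subgroup minus the effect in another. Running the model once per subgroup gives several estimates, each with its own standard error and p-value. The plan does not say how they will be compared.

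The usual informal comparison is to see where the effect is significant. That is a poor guide, because significance depends on subgroup size and on chance as well as on the effect. A component with the same benefit in everyone will often reach significance in the larger subgroup, or in one of two equal subgroups by luck, and miss it in the other. Since the findings are meant to shape later tailored interventions, a false pattern of this kind could send that work in the wrong direction.

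**Working it through.** **Inputs.** Section 5.2 gives SD 4 kg, a component effect of 0.25 SD (1 kg), 560 randomized, 10% attrition, 504 at 6 months, 252 per component level, 80% power and a two-tailed test. Section 3.3.2 gives the gender mix only as "At least half will be female". Section 4.1.3 gives ethnicity: "we plan to recruit 55% non-Hispanic Whites, 22% African Americans, 9% Hispanics, 4% other minority (45% minority"). The four listed ethnic shares sum to 55 + 22 + 9 + 4 = 90%.

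**Assumptions.** Two-sided alpha 0.05 (no value is stated), SD 4 kg in every subgroup, component levels balanced within subgroups, and equal attrition across subgroups.

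**Step 1: the plan's own figure.** At 252 per level and 0.25 SD, the noncentral t with two-sided 0.05 gives 80.0% power, and 504/(1 − 0.10) = 560. The plan's figure reproduces, which supports the assumed alpha.

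**Step 2: power within a subgroup.** The standard error of a component effect in a subgroup of size n is SD × √(4/n). For n = 252 this is 4 × √(4/252) = 0.504 kg, and power at 0.25 SD is 50.7%.

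**Step 3: how often equal effects look unequal.** With powers p and q in two independent subgroups, the chance that exactly one is significant is p(1 − q) + q(1 − p). For equal halves this is 2p(1 − p):

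| True effect in both halves | Power in each half | Exactly one significant |
|---|---|---|
| 0 | 5.0% | 9.5% |
| 0.10 SD | 12.4% | 22% |
| 0.25 SD | 50.7% | 50% |
| 0.35 SD | 79.0% | 33% |
| 0.50 SD | 97.7% | 4.5% |

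Unequal splits, all at 0.25 SD:

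| Split | Power in each subgroup | Exactly one significant |
|---|---|---|
| 60/40 | 58.2% and 42.3% | 51% |
| 70/30 | 64.9% and 33.3% | 55% |
| 80/20 | 70.7% and 23.7% | 61% |
| White vs African American, printed shares (0.55 × 504 = 277; 0.22 × 504 = 111) | 54.5% and 25.7% | 52% |
| Same, shares rescaled to 100% (308 and 123) | 59.0% and 28.0% | 54% |

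With the printed shares, the White vs African American figure at other effect sizes is 9.5% at zero, 19% at 0.10 SD, 53% at 0.35 SD and 26.5% at 0.50 SD. A simulation with 20,000 runs per setting agreed (for example, 50.2% for halves at 0.25 SD). In it, a direct test of the difference rejected 4.7–5.4% of the time throughout.

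**Step 4: what a direct comparison can deliver.** The standard error of the difference is SD × √(4/nA + 4/nB). For 252/252 it is 4 × √(8/252) = 0.713 kg, so the 95% half-width is 1.96 × 0.713 = 1.4 kg.

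| Contrast | 95% CI half-width | Power for a 0.25 SD (1 kg) difference | Difference with 80% power |
|---|---|---|---|
| 252 / 252 | 1.4 kg | 29% | 0.50 SD (2.0 kg) |
| White 277 / African American 111 | 1.8 kg | 20% | 0.63 SD (2.5 kg) |
| White 277 / Hispanic 45 | 2.5 kg | 12% | 0.90 SD (3.6 kg) |

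An 80/20 split (403/101) also has 20% power.

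**Step 5: relation to the interaction power in section 5.2.** Under −1/+1 coding, a main effect of 0.25 SD is a coefficient of 0.125 SD. The same coefficient on a moderator-by-component term is a gap between subgroup effects of 4 × 0.125 = 0.50 SD. This matches the 80% entry for equal halves. Section 5.2 therefore gives no assurance for a 0.25 SD gap between subgroups.

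**Step 6: number of tests.** Five components × four example moderators = 20 tests, at one test each. At 5% per test, 20 × 0.05 = 1 false positive is expected when no moderation exists. If the tests are independent, the chance of at least one is 1 − 0.95^20 = 64%.

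**The case against.** The strongest reply has four parts.

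1. Separate analyses of non-overlapping subgroups yield independent estimates and standard errors, so anyone can subtract them and form an interval. That is true. It means the remedy is easy, but the plan does not say the subtraction will be done.
2. The discordance figures depend on a significant-here-but-not-there reading that the plan never states. That also stands: they show what that reading would cost and are not an error rate of the plan itself.
3. The aim is labelled exploratory, moderation plays no part in choosing components, and latent class analysis is planned as well. This limits the harm but does not supply the missing comparison, and the results are still meant to guide tailoring.
4. A test of the difference is right 95% of the time only when effects are truly equal. If they differ by 0.25 SD, it misses the difference about 71% of the time at 50/50 and about 80% for White vs African American participants. That is correct, and it is why the fix rests on the interval and states its limits. A wide interval shows that the data cannot settle the question, whereas a pair of separate p-values hides this.

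The count of 20 tests is also a minimum. Two ethnicity contrasts would make it 25, and 1 − 0.95^25 = 72%.

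**Conclusion.** The concern holds. For the observed moderators, the plan asks about a difference between subgroups and specifies only within-subgroup analyses. If separate significance were the guide, a uniform effect of the size the trial is powered for would appear subgroup-specific about half the time or more (50–61% across the splits examined). The chance is smaller at the extremes: 9.5% at zero effect, and 4.5% for equal halves at 0.50 SD. These figures assume two-sided 0.05, 504 analysed, equal true effects and the significance-based reading. The sample size, Primary Aim 1 and component selection are unaffected. The change should be made, but its importance is confined to the moderation conclusions.

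**What to change.** In section 1.5 and the Secondary Aim paragraph of section 5, replace the separate analyses with moderator-by-time and moderator-by-component-by-time terms in the full-sample mixed model, one moderator at a time. Base any statement of differential response on the 6-month term and its 95% CI in kg. Keep subgroup-specific estimates from the same model as description. List the moderators consistently in both places (age is in section 5 but not in section 1.5), and say whether the component-by-component terms may also vary by moderator.

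State three limits:

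1. Power is low, with the figures in Step 4.
2. A non-significant term does not show equal effects.
3. The 5% level applies per test, so report how many tests were done and label findings hypothesis-generating.

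The cost is wording plus extra terms in a model already planned; no new data are needed. The price is wide intervals (half-widths of about 1.4 to 2.5 kg). Reaching 80% power for a 0.25 SD difference in an even split would need 16 × (1.96 + 0.84)² / 0.25² ≈ 2,010 analysed, so the limits should be declared and the trial left at its planned size.
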